## 6.7 Cycle 3 and Onwards

### 6.7.1 Day 1

- Physical examination
- Weight
- ECOG performance status ([Appendix II](#))
- Vital signs, including blood pressure, heart rate, respiration rate and temperature
- Hematology, including complete blood count with white blood cell differential
- Serum chemistry, including sodium, potassium, chloride, magnesium, CO2, BUN, creatinine, glucose, calcium, albumin, total protein, total bilirubin, AST, ALT, alkaline phosphatase
- Creatinine clearance (Cockcroft-Gault method; [Appendix I](#))
- Disease assessment per IWG 2006 criteria ([Appendix V](#)). Disease assessment is performed every two cycles (every 8 weeks) through Month 12, based on peripheral blood and/or bone marrow according to standard of care. Thereafter, disease assessment will be conducted every three cycles (every 12 weeks).

- ECG: standard 12-lead ECG with subject in a semi-recumbent position, per [Table 15](#)
- APR-548 administration
- Blood sampling for APR-548 and azacitidine PK, per [Table 13](#)
- Azacitidine administration over 7 consecutive days, on Days 1-7. S.c. route is preferred but may be given i.v. at the investigator's discretion. The same route should be maintained over the 7-day treatment period (whichever route of administration is used on Day 1, the same route should be followed on all other days).
- Blood and bone marrow for exploratory biomarker sample testing
- Serum or urine  $\beta$ hCG for female subjects of childbearing potential
- Ophthalmologic evaluation, per [Table 16](#)
- Clinical safety assessment
- Concomitant medications review
- Transfusion log

### 6.7.2 Days 2 - 7

- Vital signs, including blood pressure, heart rate, respiration rate and temperature
- APR-548 administration on Days 2-4
- Azacitidine administration on Days 2-7. On the days of concomitant administration, azacitidine is administered 1 hour after APR-548
- Clinical safety assessment
- Concomitant medications review
- Transfusion log

### 6.7.3 Day 15

- Hematology, including complete blood count with white blood cell differential
- Serum chemistry, including sodium, potassium, chloride, magnesium,  $\text{CO}_2$ , BUN, creatinine, glucose, calcium, albumin, total protein, total bilirubin, AST, ALT, alkaline phosphatase
- Creatinine clearance (Cockcroft-Gault method; [Appendix I](#))
- Ophthalmologic evaluation, per [Table 16](#) (only in Cycle 3)
- Clinical safety assessment
- Concomitant medications review
- Transfusion log

## 6.8 End of Treatment Visit

This visit should take place within 28 days of the last dose of study treatment, if treatment is stopped early for any reasons.

- Physical examination
- Weight

- Vital signs
- ECOG performance status ([Appendix II](#))
- Hematology, including complete blood count with white blood cell differential
- Serum chemistry, including sodium, potassium, chloride, magnesium, CO2, BUN, creatinine, glucose, calcium, albumin, total protein, total bilirubin, AST, ALT, alkaline phosphatase
- Creatinine clearance (Cockcroft-Gault method; [Appendix I](#))
- Disease assessment per IWG 2006 criteria ([Appendix V](#))
- Blood and bone marrow for exploratory biomarker sample testing
- Ophthalmologic evaluation per [Table 16](#)
- ECG: standard 12-lead ECG with subject in a semi-recumbent position, per [Table 15](#)
- Serum or urine βhCG
- Clinical safety assessment
- Concomitant medications review
- Transfusion log

## 6.9 Long-Term Follow-Up

Long-term follow-up can be done remotely (e.g., via telephone, via local practitioner or via review of medical records). All subjects who undergo HSCT following discontinuation of APR-548 are to be followed after the last dose until relapse or end of study. Subjects who respond and discontinue study treatment for reasons other than disease relapse should continue to have response assessments, and survival should be collected every 2 months until disease relapse, withdrawal of consent for study participation, or death, whichever occurs first. After disease relapse, data for survival should be collected every 6 months until death or withdrawal of consent for study participation. If a subject proceeds to HSCT, evaluation of the extent of disease, response to treatment, and any new antineoplastic therapies will be collected at least monthly as long as the subject remains in remission and assessed as part of the study until relapse, death, withdrawal of consent, lost to follow-up, or end of study, whichever comes first. If a subject is removed from the study due to unacceptable AEs, the event(s) will be followed until resolution or stabilization.

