Duration of Follow-Up	
Subjects will be followed as per the Schedule of Assessments.
 
After a subject is removed or withdrawn from study treatment, the subject will be followed until death or withdrawal of consent for study participation, whichever occurs first.
 
Off-treatment data on OS will be updated every 6 months or until death or withdrawal of consent for study participation, whichever occurs first. If a subject is removed from the study treatment due to unacceptable AE(s), the event(s) will be followed until resolution or stabilization of the AE(s). Subjects who respond and discontinue study treatment for reasons other than disease relapse should continue to have response assessments, and survival should be collected every 2 months until disease relapse, withdrawal of consent for study participation, or death, whichever occurs first. After disease relapse, data for survival should be collected every 6 months until death or withdrawal of consent for study participation.
 
Criteria for Removal from Study Treatment
 
Study treatment can continue for subjects deriving clinical benefit in the opinion of the investigator, unless one or more withdrawal criteria are met, or at the subject's discretion, or if the study is terminated.
 
1. Study Treatment Discontinuation
 
Study treatment must be discontinued if:
 

• There is evidence of disease progression according to IWG 2006 criteria. (Subjects who have PD but who are continuing to derive clinical benefit in the opinion of the investigator may continue to receive study treatment).

• A female subject becomes pregnant.

• A subject is non-compliant with the requirements of the protocol.

• A subject has an adverse experience that would, in the investigator's judgment, make continued participation in the study an unacceptable risk.

• The subject starts new treatment for their disease under study.

• The subject receives HSCT.

 
2. Subject Withdrawal from Study Treatment
 
If the subject is permanently withdrawn from study treatment, but does not withdraw consent from the study, the investigator should make every effort to have the subject complete all withdrawal assessments at the time of withdrawal and complete all scheduled follow-up visits.
 
3. Study Completion
 
Subject must be taken off the study if:
 

• The subject dies during the study.

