## 2.0 BACKGROUND INFORMATION

### 2.1 Disease Background

Myelodysplastic syndromes (MDS) are a heterogeneous group of neoplasms arising from a clonal hematopoietic precursor. MDS is characterized clinically by cytopenia and a tendency to transform to acute myeloid leukemia (AML). Prognostic scoring systems have been developed to help stratify patients based on predicted survival and progression to AML. In practice, treatment decisions are made by grouping patients with MDS into lower and higher risk subgroups as defined by clinical prognostic scoring systems. Specifically, the International Prognostic Scoring System (IPSS) and its more modern version, the revised-IPSS (IPSS-R), represent the most widely used clinical prognostic tools. Those patients that fall in the higher risk group have an expected survival of less than 12 months if left untreated and progress to AML greater than 30% of the time.

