#### **4.1.1 Treatment Duration**

Subjects may continue treatment with APR-548 and azacitidine until disease progression, development of other unacceptable toxicity, confirmed pregnancy, HSCT, death, withdrawal of consent, or study termination, whichever occurs first. Subjects who experience disease progression per the applicable response criteria who are, in the opinion of the investigator, benefiting from treatment, may be allowed to continue on study drug with approval of the Medical Monitor.

Following discontinuation of study drug, subjects are to attend a follow-up visit 28 days after the last dose of study drug for final assessments. When study drug is withheld from a subject in order to resolve a toxicity and the subject does not subsequently restart treatment, end of treatment is defined as the date when the study drug was first held. Subjects should proceed with end of treatment assessments, safety, and survival follow-up. If the decision to not restart study treatment comes outside of the 28-day safety follow-up window, the subject should have an End of Treatment visit and proceed with survival follow-up.

Subjects who achieve an adequate response to treatment with APR-548 and meet other criteria required to undergo HSCT may proceed to HSCT after discontinuation of APR-548. If a subject proceeds to HSCT, evaluation of the extent of disease, response to treatment, and any new antineoplastic therapies will be collected at least monthly as long as the subject remains in remission and assessed as part of the study until relapse, death, withdrawal of

consent, loss to follow-up, or end of study, whichever comes first. If a subject discontinues APR-548 to undergo HSCT, but is then deemed ineligible for HSCT, the subject may restart APR-548 with Medical Monitor approval.

All subjects that enter survival follow-up will be contacted every two months for assessment of survival status and new antineoplastic therapies. Please see Section [6.9](#) for details on long-term follow-up.

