## 8.6 Efficacy

CR rate will be summarized for the safety and EE subjects as the proportion (%) of subjects with CR. In addition to presenting the CR rate, its associated exact 95% CI for each treatment arm will also be presented.

DOR is defined as the time from the date when criteria for response are met to the date of PD or death due to any cause, whichever occurs first. Subjects alive with no PD will have their DOR censored at the date of the last clinical assessment. The DOOR will be summarized in each treatment arm by providing the median DOR together with associated 95% CI, using Kaplan-Meier methodology.

Overall response will be summarized in number (%) of subjects in each category of responses (CR, PR, mCR with HI, mCR without HI, HI). ORR will be analyzed by using the similar method as primary endpoint CR. DOR, as defined above, will also be evaluated in regard to ORR. Time to AML is calculated from first day of study treatment to first onset of AML. Kaplan-Meier methodology will be utilized. Rate of AML transformation will be analyzed by using the similar method as primary endpoint CR.

Survival data are collected at treatment and follow-up periods. Subjects will be followed until death or withdrawal of consent from the study, whichever occurs first.

OS is defined as the number of days from the first day of treatment to the date of death due to any cause. Kaplan-Meier methodology will be utilized.

RFS is defined as the time from the date of randomization to disease relapse or death, whichever occurs first. If neither event occurs, RFS will be censored at the date of the last clinical assessment. Kaplan-Meier methodology will be utilized.

Time to AML, OS and RFS will be analyzed using the similar methods as DOR.

Transition rate to HSCT will be analyzed using the similar methods as CR.

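### AML that first appears after the End of Treatment visit is not collected for subjects in survival-only follow-up, so the reported AML rate can only err downward

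*Combined protocol and SAP*

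**What the plan says.** **Endpoint.** Rate of and time to AML, by WHO criteria, is secondary objective 1e (section 3.2) and secondary endpoint 5 (section 8.3.2). Time to AML runs from the first day of study treatment.

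**Follow-up after treatment.** Section 6.9, repeated in substance in the synopsis and in footnote y of Table 12, sets out three situations:
- Responders: "Subjects who respond and discontinue study treatment for reasons other than disease relapse should continue to have response assessments", until relapse, withdrawal of consent or death.
- HSCT recipients: "All subjects who undergo HSCT following discontinuation of APR-548 are to be followed after the last dose until relapse or end of study". Disease evaluation is at least monthly while they remain in remission.
- After relapse: "After disease relapse, data for survival should be collected every 6 months until death or withdrawal of consent for study participation".

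Section 4.1.1 adds: "All subjects that enter survival follow-up will be contacted every two months for assessment of survival status and new antineoplastic therapies". The synopsis (Duration of Follow-Up) says: "Off-treatment data on OS will be updated every 6 months". In Table 12, Survival is the only item marked for long-term follow-up.

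**Last common assessment.** The End of Treatment visit in section 6.8 includes an IWG 2006 disease assessment. On timing it says: "This visit should take place within 28 days of the last dose of study treatment, if treatment is stopped early for any reasons".

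**Analysis.** Section 8.6: "Rate of AML transformation will be analyzed by using the similar method as primary endpoint CR". For CR that means a proportion with an exact 95% CI. Section 8.2 makes the safety population (at least one dose of APR-548) primary for efficacy. Section 8.6 also plans a Kaplan-Meier time to AML by methods similar to those for DOR, which censor at the last clinical assessment.

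**The concern.** The endpoint counts AML from first dose with no end date short of death or the end of the study, but the data that could show AML stop earlier for some subjects than for others. Observation ends at a disease-related moment: stopping without a response, or relapse. A subject who leaves treatment AML-free and transforms two months later remains in the denominator and is counted as not having transformed.

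The reported rate would then depend partly on how long subjects stayed under disease assessment, not only on how often they transformed. This matters when the figure is carried into a later protocol or set beside published rates obtained with different follow-up.

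**Working it through.** **Step 1. Who is observed for AML, and until when.**

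| Group | Disease status collected until | Afterwards |
|---|---|---|
| Any subject on treatment | Every two cycles to Month 12, then every three, and whenever progression is suspected (Table 12, footnote l) | End of Treatment assessment (section 6.8) |
| Responder who stops without relapse | Relapse, withdrawal or death | Survival every 6 months after relapse |
| HSCT recipient | End of remission | No AML item listed |
| Non-responder who stops | End of Treatment assessment | Survival and new therapies (section 4.1.1) |

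The gap is therefore AML that first arises after the End of Treatment assessment in non-responders, or after the relapse assessment in responders and HSCT recipients. AML seen at any of those assessments is captured.

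**Step 2. Whether safety reporting fills the gap.** Section 7.1.2.1 ends AE and SAE reporting 30 days after the last dose and exempts events unequivocally due only to progression from separate AE entry. Section 7.1.2.6 asks for later SAEs only if the investigator considers them treatment-related. Neither route yields AML status.

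**Step 3. Direction of the bias in the proportion.** Let N be the denominator, T the subjects who truly transform, and M those among T whose AML first arises when disease status is no longer collected.

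Reported rate = (T − M)/N; true rate = T/N; difference = −M/N.

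M cannot be negative, so the error is downward or zero. The synopsis gives the maximum N as 6 × 6 + 10 = 46, which reproduces. At that size each missed case costs 1/46 = 2.2 percentage points.

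**Step 4. Hypothetical size.** The documents state no expected AML rate, event count or follow-up length for this trial. The only anchor is section 2.1, on untreated higher-risk MDS: "progress to AML greater than 30% of the time". The true counts below (roughly 20%, 30% and 40%) and the missed counts (roughly a quarter, a half and three quarters) are assumptions.

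| True AML | Missed | Reported |
|---|---|---|
| 9/46 = 19.6% | 2, 4, 7 | 15.2%, 10.9%, 4.3% |
| 14/46 = 30.4% | 4, 7, 10 | 21.7%, 15.2%, 8.7% |
| 18/46 = 39.1% | 4, 9, 14 | 30.4%, 19.6%, 8.7% |

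For the middle row, the exact 95% CI is 17.7 to 45.8% with nothing missed, then 10.9 to 36.4%, 6.3 to 28.9% and 2.4 to 20.8%.

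**Step 5. What drives the size.** If only non-responders lost observation:

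shortfall = (1 − ORR) × (AML risk in non-responders) × (share of their AML arising after the last assessment).

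Take ORR at 47 to 60% (the azacitidine figures in section 2.4, as a stand-in) and assume a risk of 30 to 50% and a late share of 25 to 75%.
- Smallest: 0.40 × 0.30 × 0.25 = 3.0 points.
- Largest: 0.53 × 0.50 × 0.75 = 19.9 points.

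Relapsed responders would add to this. The risk and the late share have no source in the documents.

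**Step 6. Time to AML.** Under the DOR rule, subjects in survival-only follow-up are censored at their last clinical assessment. Because stopping or relapse is linked to the state of the disease, this censoring is likely informative. No rule is given for death before AML. If such deaths are censored, one minus the Kaplan-Meier estimate overstates cumulative incidence, the opposite direction to unseen AML. The net direction of error in that curve is therefore unknown.

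**The case against.** The strongest case on the other side has four parts.

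1. **Most AML may be seen.** Every subject who stops should have an End of Treatment disease assessment. Assessments are also made whenever progression is suspected, and sections 4.1.1 and 4.4 let subjects continue treatment after progression if they benefit. This stands as a limit on the gap. A reader might infer that AML in non-responders is never collected, or that non-responders are the only group affected. The documents support neither: AML up to the End of Treatment assessment is captured, and relapsed responders and relapsed HSCT recipients lose observation too.

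2. **New therapies are recorded.** Under section 4.1.1 a new antineoplastic therapy could prompt a query. It is an indirect signal without diagnosis or date, and it misses subjects who receive no further therapy.

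3. **Little depends on the endpoint.** This is a single-arm dose-finding trial. AML is one of several secondary endpoints, no hypothesis is tested on it, and escalation and the RP2D rest on DLTs, exposure and the mBED. With 46 subjects the interval is wide: 21.7% lies well inside 17.7 to 45.8%. This stands, and it limits the importance of the point. A confidence interval covers sampling error only, however, and would be built around a count that is too low.

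4. **Kaplan-Meier is also planned.** It does not count unseen subjects as AML-free, which helps, but likely informative censoring and the unhandled competing event of death remain.

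**Conclusion.** The gap is real and its direction in the simple proportion is certain: zero or downward. It covers AML first arising after disease status ceases to be collected, in non-responders who stop and in responders or HSCT recipients after relapse. This rests on the text of sections 4.1.1, 6.8, 6.9 and 8.6 and needs no assumed numbers.

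The size cannot be computed from the documents. The percentages above are hypothetical and show only that the shift could be small or large. Three stronger readings should be resisted:
- **A definite figure for the bias.** One might build it from the 30% in section 2.1 and the median OS of 5 to 9 months in section 2.2. The 30% concerns untreated patients, and the documents give neither time to stopping nor AML risk by response.
- **Non-responders are the subjects most likely to transform.** This is plausible, but no figure in the documents shows it.
- **The combination would appear to protect against AML.** The trial has no comparator, so this could arise only through comparison with outside rates.

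Dose finding and the primary endpoints are unaffected. The point is worth acting on because the correction is cheap and the missing data are hard to recover later.

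**What to change.** 1. **Collect AML status for everyone.** In sections 4.1.1 and 6.9, the long-term follow-up column and footnote y of Table 12, and the synopsis, add AML transformation (yes/no, date, source, and blast percentage where already available) to the planned contact. Apply it to all subjects until death, withdrawal of consent or end of study.

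2. **State one AML definition.** Endpoint 5 uses WHO criteria, and section 2.10 places WHO-defined MDS below 20% blasts. Appendix V puts transformation at 30% or more. A subject between these values could be classified either way, so a yes/no field needs this settled first.

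3. **Reconcile the contact intervals.** Section 4.1.1 gives two months for all subjects in survival follow-up. The synopsis gives 6 months for off-treatment survival. Section 6.9 gives 2 months for responders and 6 months after relapse. This conflict does not cause the bias, but the interval determines how well AML can be dated.

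4. **Change the analysis in section 8.6.** Estimate AML by cumulative incidence with death as a competing event, censoring at the last date on which AML status was known. If a crude proportion is kept, label it as AML observed up to the last disease assessment.

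**Cost.** A protocol amendment and a few eCRF fields at a contact that section 6.9 already allows by telephone or record review. No extra visit or marrow is needed, so blast percentage will often be blank. Data entry rises slightly, and the reported AML rate may be less favourable.

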# 7.0 STUDY ASSESSMENTS

## 7.1 Safety Assessments

### 7.1.1 Safety Analysis

Safety data will be tabulated for all subjects and include vital signs, laboratory parameters, ECG and AEs.

## 7.1.2 Reporting of Adverse Events

### 7.1.2.1 Adverse Events

An AE is any untoward medical occurrence in a subject administered a pharmaceutical product that does not necessarily have a causal relationship with the treatment. An AE can be any unfavorable and unintended sign (including a laboratory finding), symptom or disease temporally associated with the use of a medicinal (investigational) product, whether or not related to the medicinal (investigational) product.

The AE reporting period starts at the time of study treatment initiation. At each evaluation, subjects should be interviewed in a non-directed manner to elicit potential adverse reactions from the subject. The occurrence of an AE will be based on changes in the subject's physical examination, laboratory results, and/or signs and symptoms.

For the time period from signing of informed consent up to receipt of the first dose of APR-548, non-serious events should be recorded as medical history on the appropriate eCRF page within the clinical database. SAEs that occur during the screening period are required to be reported and should include an assessment on whether the SAE was related to a protocol-defined procedure or activity.

All AEs (except laboratory abnormalities that are assessed as not clinically significant by the investigator, or examining ophthalmologist as applicable), regardless of causal relationship, are to be recorded in the eCRF and source documentation. The investigator must determine the intensity of any AEs according to the NCI-CTCAE version 5.0 and their causal relationship to each study medication administered that has been administered to the subject at the time of event onset. Those AEs not covered by these criteria will be graded as follows:

1. Mild: Discomfort noticed, but no disruption of normal daily activity. Prescription drug not ordinarily needed for relief of symptom but may be given because of personality of subject.
2. Moderate: Discomfort sufficient to reduce or affect normal daily activity. Subject is able to continue in study; treatment for symptom may be needed.
3. Severe: Incapacitating, severe discomfort with inability to work or to perform normal daily activity. Severity may cause cessation of treatment with test drug; treatment for symptom may be given and/or subject hospitalized.
4. Life-Threatening: Symptom(s) place the subject at immediate risk of death from the reaction as it occurred; it does not include a reaction that, had it occurred in a more serious form, might have caused death.
5. Fatal: Event caused the death of the subject.

AEs will be followed until resolution or stabilization while the subject remains on-study. Once the subject is removed from study, events thought to be related to the study medication will

be followed until resolution or stabilization, unless, in the investigator's opinion the event is unlikely to resolve due to the subject's underlying disease, or until the subject starts a new treatment regimen or the subject is lost to follow-up.

The end of the AE and SAE reporting period is 30 days after last dose of study treatment, unless the subject has withdrawn consent for study participation or started new therapy for underlying disease. Progression of primary disease should be reported on a response assessment eCRF in this FIH study. Events unequivocally related only to progression of primary disease do not need to be reported separately on the AE CRF page. Hospitalization to start new therapy for primary disease after confirmed progression/relapse does not meet reporting criteria for an AE or SAE.

